Blood sampling for genotyping for FBR (if consented)	X															
Blood sampling for RNA and serum collection for FBR (if consented)		X		X				X		X			X	X	X	
CSF sampling for FBR (if consented) 			X		X			X								

V=visit; T=telephone call; EoT = End of Trial; W=Week; D=Day  
\*First dosing

1. If a patient is withdrawn from the study or discontinues study treatment, will be asked to return to the clinic and the procedures as depicted for the End-of-Trial visit will need to be done. The first 100 patients (1/3 of the total study population) will continue study participation until week 72 (Visit 8), or until reaching an intercurrent event. For all other patients (2/3 of the study population) the end of the study will be the week 48 (visit 6) of each patient (or an intercurrent event).
2. If a patient does not participate in the extended follow-up study, treatment is to be continued until the EoT visit. The EoT visit should also be performed cessation. If a subject roll over to the extended treatment study, treatment will take place between 1 and 14 days after treatment 7-14 days after study termination in case of withdrawal or early terminating of the study.
3.  $\beta$ -hCG in plasma and urine pregnancy test should only be performed in women of childbearing potential.
4. Possible peripheral nerve dysfunction (= sensory or motor symptoms), diminished or absent reflexes (compared with baseline examination), sensory abnormalities (e.g. numbness or tingling) or weakness on neurological examination will be monitored during the study. In case a subject experiences clinical signs or symptoms at home, subjects will be asked to contact the clinic.

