**Visit 8 Week 72 (Day 504 ±7Days)-End of Trial visit (first 100 patients enrolled)**

The following procedures will be performed:

- Review ongoing concomitant medications
- Complete physical examination
- Neurological examination
- Weight
- Vital signs measured with the subject in a supine/semi-supine position (for at least 5 minutes prior), including blood pressure, pulse rate, pulse oximetry and temperature
- Standard 12-lead ECG (subject should be in a supine/semi-supine position for at least 5 minutes prior to assessment)

- Fasting blood samples for routine clinical labs (clinical chemistry, haematology). See table 2 for lab assessments
- Urine samples for urinalysis
- Urine pregnancy test only in women of childbearing potential
- Plasma vitamin B6 levels, and, if necessary, vitamin B6 supplements (pyridoxine (100 mg/day)) will be prescribed
- ALS evaluation procedures: ALSFRS-R, Slow Vital Capacity (SVC), Hand-Held Dynamometry, ALSAQ-40, Edinburgh Cognitive and Behavioural ALS Screen (ECAS), EQ-5D-5L, VAS, and King's staging system and MiToS
- Blood sampling for biomarker: neurofilament light (NFL). Creatinine and creatine kinase will be measured in routine biochemistry lab testing.
- Urine collection for biomarkers: urinary extracellular domain of neurotrophin receptor p75 (Urinary P75ECD) and oxidative stress biomarker 8-hydroxyguanosine (8-OHdG)
- Blood sampling for RNA and serum collection for FBR (if consented)
- Blood sampling for FAB122 (if early withdrawal)
- Nerve Conduction Study (NCS) (if required)
- Adverse Events monitoring
- Cost questionnaire
- Compliance check

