- ALT/AST  $\geq$  5xULN and ALT/AST  $<$  8xULN that persists more than two weeks

8-Acute lung injury with pyrexia, cough, dyspnoea and chest X-ray abnormality

9-Rhabdomyolysis

10-Disseminated intravascular coagulation (DIC)

11-Hypersensitivity reaction

12- Anaphylactic reaction/shock

13- Thrombocytopenia

14- Neutropenia

15-Introduction of riluzole

16-The subject cannot attend two consecutive study visits and key safety assessment cannot be performed

If a subject discontinues the trial for safety reasons, a PK sample is to be taken (with the time of sampling after last dosing clearly documented) in those sites participating in the PK sub study.

In case a subject withdraws FBR consent, the blood samples taken for FBR will be destroyed (when not analysed yet).

The sponsor reserves the right to terminate the study at any time if continuation of the protocol would present a potential safety risk to the subjects.

Every effort will be made to ensure that patients who do not complete all study requirements return to the site for the End-of-Trial Visit. Patients who withdraw due to an Adverse Event (AE) or Serious Adverse Event (SAE) will be given appropriate care under medical supervision until the symptoms resolve or the patient's condition becomes stable. The End-of-Trial Visit will be performed 7-14 days after withdrawal and the same procedures as Visit 8 will be performed.

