The primary strategy for handling the IE will consist of the "Treatment Policy" strategy applied for all these intercurrent events, i.e., the efficacy observed assessment will be used regardless of the intercurrent event. Therefore, overall the amount of missing data generated will be a very small. For these cases a placebo (copy from reference) multiple imputation will applied. A total of 20 imputed data sets will be created.

However, it is noted that the "Treatment Policy" strategy will not be applicable for terminal intercurrent events such as death (IE #g) or when there are real lost to follow-up cases after doing all efforts to retrieve the data (some cases in IE #f). For cases with missing data in IE #f, the same general approach as described above will be implemented. For related death (IE #g) it is proposed to use a "Composite strategy" and thus a conservative scenario using a 95th worst percentile combined with multiple to avoid variance artefactual shrinking.

---

- h. Population-level summary: the change from baseline in ALSFRS-R score after 48 weeks (primary time point), using a linear mixed modelling for repeated measures. The model will include factors for treatment, time, treatment-by-time interaction, and concomitant use of riluzole (yes/no) as fixed effects and baseline ALSFRS-R score and slope of disease progression (based on change in ALSFRS-R score) as (random) covariates (see section 11.3.4.1)).

To evaluate the impact of missing data and of the handling methods, a number of sensitivity analyses will be performed for the primary endpoint:

- **As treatment multiple imputation:** For any subject with missing values, the estimates for the missing assessments will be based on the actual treatment group of that subject. One hundred imputations will be performed.

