### **5.6.1 Primary analysis**

The primary endpoint is defined as the change from baseline in total ALSFRS-R score after 48 weeks (primary timepoint).

For the primary analyses, a placebo (reference) multiple imputation (pMI) will be applied to impute missing data for any patients (i.e. from both treatment arms) who discontinue treatment early, irrespective the reason for drop-out (only when due to intercurrent events with unknown cause), and for which no data was collected after treatment discontinuation. The pMI method assumes the statistical behavior of placebo- and drug-treated patients after dropout is the statistical behavior of placebo-treated patients. A total of 20 imputed data sets will be created.

Before applying the statistical model to the primary endpoint, intercurrent events will be handled following the rules specified in Section 5.2.

The primary endpoint will be analyzed using a mixed model for repeated measures (MMRM), considering ALSFRS-R is assessed at multiple timepoints. The average treatment effect (lsmeans) and the treatment difference (estimand) of the change from baseline ALSFRS-R total score at 48 weeks will be extracted from the results from this model and presented together with the 95% confidence interval and p-value. Other timepoints will also be presented.

The model will include factors for treatment, time, treatment-by-time interaction, the stratification factor concomitant use of riluzole (yes/no), baseline ALSFRS-R score and the stratification factor slope of disease progression as fixed effects. An unstructured (UN) covariance matrix will be used in the model. If the model does not converge, the structure will be adapted to respectively AR(1), Toeplitz or Compound Symmetry (CS). The results of the 20 imputed data sets will be combined to obtain the final estimate of the treatment difference with 95% confidence interval and p-value.

An example SAS code which can be used as basis is as follows:

```
proc mixed data=<data>;
  class trt time riluse;
  model cfb=trt time trt*time riluse base disslope / ddfm=kr;
  repeated time/ subject=patient type=un;
  lsmeans trt*time/cl;
run;
```

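### Placebo imputation excludes any early stopper with a later score, so a patient who attends the End-of-Trial visit and then leaves has no stated rule for week 48

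*SAP*

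**What the plan says.** **The imputation trigger.** SAP 5.6.1 reserves pMI for patients who discontinue early "and for which no data was collected after treatment discontinuation". Protocol 11.3.4.2 has the same condition. The SAP adds a second limit: "irrespective the reason for drop-out (only when due to intercurrent events with unknown cause". It also states what pMI assumes: after drop-out, patients from both arms behave like placebo patients.

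**The End-of-Trial visit.** Under protocol Table 1, footnote 1, a patient who withdraws or stops study drug "will be asked to return to the clinic and the procedures as depicted for the End-of-Trial visit will need to be done". Protocol 6.5 adds: "The End-of-Trial Visit will be performed 7-14 days after withdrawal and the same procedures as Visit 8 will be performed". The Visit 8 list includes "ALS evaluation procedures: ALSFRS-R, Slow Vital Capacity (SVC), Hand-Held Dynamometry, ALSAQ-40". SAP 5.3 generally maps an early-termination score to the next protocol visit at which that assessment is due.

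**Rules elsewhere.**
- Protocol 11.4, on the missing data that remain under the treatment-policy strategy: "For these cases a placebo (copy from reference) multiple imputation will applied". It does not require that no later data exist.
- SAP 5.2 gives deaths and real losses to follow-up a 95th-worst-percentile value. A real loss is one where attempts to contact the patient and retrieve data have failed.
- SAP 5.6.2 sends any surviving patient with a missing week-48 score to the 5.6.1 imputation before CAFS is derived.
- SAP 5.2 names imputation from the patient's own treatment group as a MAR sensitivity analysis.

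**The concern.** One visit soon after stopping is enough to make the no-data condition false. A patient who withdraws at week 20, gives one off-drug ALSFRS-R score and then leaves has post-discontinuation data but nothing at week 48. If the condition is programmed as written, pMI skips that patient and the gap goes into the MMRM. The MMRM fills it implicitly from the patient's own arm, most of whom are still on drug.

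That is the opposite of the assumption stated for pMI, and it credits FAB122 with benefit that keeps building after the drug is stopped. Two programmers could also derive different primary estimates from the same text. Because CAFS borrows the 5.6.1 imputation, the ambiguity reaches step II of the confirmatory hierarchy.

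**Working it through.** **1. Who falls between the rules.** ALSFRS-R is due at week 4 and every four weeks to week 48 (protocol 8.1.1), so an early-termination score normally reaches week 48 only after a withdrawal later than about week 44.

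| Patient, alive at week 48 | pMI as worded | Composite rule | Week 48 |
|---|---|---|---|
| Stops drug, followed to week 48 | not needed | no | observed |
| Stops drug, no later score, traceable | yes, subject to the cause parenthesis | no | pMI |
| Cannot be traced | – | yes | 95th worst percentile |
| Attends End-of-Trial visit, then leaves traceably before about week 44 | no | no | no stated rule |
| Removed alive for respiratory insufficiency (protocol 6.5, 8.1.2), attends End-of-Trial visit | no | no | no stated rule |

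**2. The plan's design figure.** Inputs (SAP 2.4): difference 3.0, SD 7.5, 2:1, two-sided 5%, 90% power.
- Placebo n = (1.960 + 1.282)² × 7.5² × (1 + 1/2) / 3.0² = 98.5, so 99 + 198 = 297 against 300 stated.
- Standard error with 200 and 100 patients = 7.5 × √(1/200 + 1/100) = 0.919. Power = 90.4%. The plan's figure reproduces.

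**3. Treatment-policy value.** Protocol 11.4 expects active-arm stops of 7% for adverse events and 10% for lack of efficacy, 17% in total (control: 3% + 5% = 8%). Assumptions: benefit accrues linearly, stops accruing when drug stops, and stops are uniform over weeks 6 to 40 (mean 23).

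3.0 × [1 − 0.17 × (1 − 23/48)] = 2.73 points.

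**4. Own-arm against placebo-based filling.** Two simulations were run, each keeping one off-drug score per leaver. Simulation A: 300 trials of 200:100, placebo decline 11.0, SD 7.5, stops 17% v 8% at weeks 6 to 40. Simulation B: large-sample random slopes, placebo decline 12, SD 7.5 at week 48, residual SD 2 to 4, active-arm stops only, weeks 12 to 36, all stoppers leaving.

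| Scenario | Treatment-policy value | Own arm | Placebo-based | Own arm − value | Own arm − placebo-based |
|---|---|---|---|---|---|
| A, all stoppers leave | 2.764 | 3.008 | 2.798 | 0.244 | 0.210 |
| A, half leave | 2.629 | 2.754 | 2.656 | 0.125 | 0.098 |
| B, 10% stop | 2.83–2.88 | 2.97–3.02 | 2.91–2.97 | 0.13–0.14 | 0.03–0.10 |
| B, 17% stop | 2.73–2.76 | 2.97–2.99 | 2.80–2.91 | 0.23–0.24 | 0.06–0.17 |

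The two treatment-policy values in A should be equal, since that quantity cannot depend on who later leaves. They differ by Monte Carlo noise (about 0.919/√300 = 0.05 per mean) around the 2.73 of step 3. The within-row differences are the usable results. B uses the fully on-drug active mean for own-arm filling, an approximation to the MMRM.

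**5. Scale.** 0.125/0.919 = 0.14 and 0.244/0.919 = 0.27 of one standard error.

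**The case against.** Much of the opposing case stands.

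- **Numbers affected.** A reader might infer that almost every drop-out is caught. The documents do not support that. Attendance is only sought: "Every effort will be made to ensure that patients who do not complete all study requirements return to the site", and no rate is given. Patients who only stop drug stay on schedule, with ALSFRS-R by telephone if needed, so many may have a week-48 score. Protocol 11.4 expects little missing data.
- **Own-arm filling is not SAP text.** A reader might infer that the SAP prescribes it. It does not: it is the MMRM's default when no rule applies. The no-data phrase could even be read visit by visit, which would fit protocol 11.4. That makes the text ambiguous, which is itself the defect in a pre-specified primary analysis.
- **The composite rule.** Patients who leave and cannot be traced get a penalised value whether or not an End-of-Trial score exists. But a consent withdrawal after an attended visit, or a removal for respiratory insufficiency, is not a failed attempt at contact.
- **The cause parenthesis.** In the SAP it may already exclude stoppers with a known cause, so for them the no-data phrase adds nothing. Protocol 11.3.4.2 has no such parenthesis, and the gap remains if it is deleted.
- **Sensitivity analyses.** The hybrid approach placebo-imputes the missing weeks of adverse-event and lack-of-efficacy stoppers without the no-data condition, and the tipping-point analysis shifts imputed FAB122 values. Neither fixes the primary estimate, and the hybrid fills all other gaps by treatment group.

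**Conclusion.** The defect is real but limited. Followed literally, the trigger leaves a definable group with no stated week-48 rule, and the MMRM default for them contradicts SAP 5.6.1's own assumption, protocol 11.4 and the CAFS rule.

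Under the assumptions above, own-arm handling overstates the treatment-policy effect by about 0.1 to 0.2 points and exceeds placebo-based filling by 0.03 to 0.2 points. This rests on 10% to 17% active-arm stops, benefit that ceases to accrue off drug, and half or all of the stoppers leaving after one score. The all-leave case is an upper scenario, because the protocol plans to follow stoppers; the documents do not give the actual share.

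Two larger inferences are not supported. The first is false-positive inflation: with no drug effect the arms do not differ, so own-arm and placebo filling agree on average. The second is a half-point bias (3.0 × 0.17 = 0.51). That needs all 17% to leave and all earlier benefit to vanish at once, whereas protocol 11.4 specifies copy from reference, and the off-drug score also enters the model.

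**What to change.** Before unblinding, replace the trigger in SAP 5.6.1 and protocol 11.3.4.2 with:

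> pMI is applied to every scheduled ALSFRS-R visit up to week 48 after treatment discontinuation that has no observed score, whether or not other post-discontinuation scores exist, unless the composite rule of Section 5.2 applies; observed post-discontinuation scores are used as they are and condition the imputation.

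In the protocol, the cross-reference should name the SAP section. Also:

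- State which analysis rule covers patients removed alive for respiratory insufficiency.
- Reconcile the unknown-cause parenthesis in SAP 5.6.1 with the statement beside it that the reason for drop-out does not matter: delete it or define it.

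The cost is a few sentences and a small programming change, with no new data. It also brings the primary rule into line with protocol 11.4 and the CAFS rule in SAP 5.6.2. The downside for the sponsor is that the estimate may become slightly less favourable to FAB122.

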##### **11.3.4.2. Primary Efficacy Endpoint**

The primary endpoint is defined as the change from baseline in ALSFRS-R score after 48 weeks (primary time point).

For the primary analyses placebo (reference) multiple imputation will be applied to impute missing data for any subjects (i.e. from both treatment arms) who discontinue treatment early, irrespective the reason for drop-out, and for which no data was collected after treatment discontinuation. A total of 20 imputed data sets will be created.

Linear mixed modelling for repeated measures will be applied on each of the imputed data set to estimate the average (lsmeans) treatment effects and the treatment difference (estimand) of the change from baseline of ALSFRS-S score at week 48.

The model will include factors for treatment, time, treatment-by-time interaction, and concomitant use of riluzole (yes/no) as fixed effects and baseline ALSFRS-R score and slope of disease progression (based on change in ALSFRS-R score) as (random) covariates.

The results of the 20 imputed data sets will be combined to obtain the final estimate of the treatment difference with 95% confidence interval and p-value.

The primary analysis will be performed on the modified intent-to-treat population (mITTs), i.e. all randomized patients who had at least one treatment intake

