- **Tipping-point analysis:** The tipping point is defined as the difference in the change from baseline in ALSFRS-R score at week 48 between FAB122 and placebo at which the study conclusion (i.e. the statistical significance) changes. To find this tipping point a systematic shift will be applied to the (as-treated) imputed values (i.e. a MNAR adjustments in the multiple imputation process) in the FAB122 treatment arm. These shifts will cover a large enough range, in steps of 0.2 to find the value for which the analyses shows a change of in significance of the primary hypothesis test, the tipping point. For each shift the primary analysis method will be repeated on the 20 multiple imputed data sets. In case such a tipping point has an unrealistic value, this will increase the confidence of the primary analysis.
- **Hybrid approach:** With the hybrid approach the missing weeks for subjects who discontinued due to AE or lack of efficacy will be imputed using placebo-based pattern imputation under the MNAR assumption. All other discontinuation/missing will be imputed using multiple imputation by treatment group using a multivariate step-wise approach using a fully conditional specification (FCS) regression method (Rubin, 1987). Missing baseline values if any, will be imputed using age and time since diagnose. Subsequent visits will be imputed using data of all previous weeks in a stepwise fashion. One hundred imputations will be performed.
- **Completer analysis:** This analysis includes only subjects who have completed the study up to week 48.
- **Per Protocol and ITT Analysis:** This analysis will include subjects from the PP and the ITT analysis sets.

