## 2.4 Sample size

The sample size estimation is based on the primary endpoint: the change from baseline in ALSFRS-R score after 48 weeks. A difference of 3.0 points between FAB122 treatment arm and placebo is assumed with a (pooled) standard deviation of 7.5 and an allocation ratio of 2:1 (FAB122:Placebo). With these assumptions, a total sample size of 300 (200 patients on FAB122 and 100 on placebo) is needed to achieve 90% power to detect the difference of 3.0 points between the two treatment groups at a 5% (2-sided) level of significance.

For further details on the background of these assumptions, refer to the protocol.

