### ***Efficacy data – missing***

To evaluate the impact of missing data and of the earlier handling methods, a number of sensitivity analyses will be performed for the primary endpoint utilizing the primary analysis population (mITT).

- **As treatment multiple imputation:** For any patient with missing values, the estimates for the missing assessments will be based on the actual treatment group of that patient. One-hundred imputations will be performed. A predicted mean matching based on a monotone regression (in case the missing data pattern is monotone) or on a fully conditional specification regression (in case the missing data pattern is arbitrary and non-monotone) will be applied. The predicted mean matching method imputes an observed value which is closest to the predicted value from the simulated regression model for each missing value. It ensures that imputed values are plausible and might be more appropriate than the regression method if the normality assumption is violated. The regression model will condition on observed values of the primary outcome measured at other time points (including baseline measurements) and possible other covariates that are related to the missing data pattern and/or primary endpoint. The statistical model for the primary endpoint will then be applied to each imputed dataset separately. The estimated parameters will be pooled using Rubin’s combining rules. This analysis will be applied under the assumption of data missing at random (MAR).

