- **Tipping-point analysis:** The tipping point is defined as the difference in the change from baseline in ALSFRS-R score at week 48 between FAB122 and placebo at which the study conclusion (i.e. the statistical significance) changes. This analysis is done to explore the impact of MNAR data and is therefore a sensitivity analysis under the assumption of MNAR. Missing data are imputed over a range of possible scenarios for treatment effect, in order to identify the scenario (or tipping point) that reverses the study conclusion as obtained in the original MAR/MCAR analysis. To find this tipping point a systematic shift will be applied to the (as-treated) imputed values (i.e. a MNAR adjustments in the multiple imputation process) in the FAB122 treatment arm. These shifts will cover a large enough range, in steps of 0.2 to find the value for which the analysis shows a change in significance of the primary hypothesis test, the tipping point. For each shift the primary analysis method will be repeated on the 20 multiple imputed data sets. In case such a tipping point has an unrealistic value (as per clinical decision), this will support the treatment effect found in the primary analysis.

---

 All deaths (including unrelated) are meant here, as it is safe to assume all deaths are related to ALS. In case of unrelated deaths, this will be very small number.

- **Hybrid approach:** With the hybrid approach the missing weeks for patients who discontinued due to AE or lack of efficacy will be imputed using the placebo-based pattern imputation under the MNAR assumption and under the assumption of monotone missing data. All other discontinuation/missing will be imputed using multiple imputation by treatment group using a multivariate stepwise approach using a fully conditional specification (FCS) regression method (Rubin, 1987), assuming the missing data pattern is arbitrary and non-monotone. Missing baseline values, if any, will be imputed using age and time since diagnose. Subsequent visits will be imputed using data of all previous weeks in a stepwise fashion. Twenty imputations will be performed.
- **Completer analysis:** This analysis includes only patients who have completed the study up to week 48, and those patients who died prior to 48 weeks assuming they would otherwise have completed the study up to 48 weeks.

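### The primary analysis pools 20 imputed data sets with no stated random seed, so a result close to p = 0.05 may not be reproducible (minor; free to fix)

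*SAP*

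**What the plan says.** **Primary analysis.** SAP 5.6.1: "A total of 20 imputed data sets will be created". Protocol 11.3.4.2 agrees: "The results of the 20 imputed data sets will be combined to obtain the final estimate of the treatment difference with 95% confidence interval and" a p-value. Protocol 11.4 repeats the figure of 20.

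**As-treated imputation (sensitivity).** SAP 5.2: "One-hundred imputations will be performed". The protocol also has 100.

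**Hybrid approach (sensitivity).** SAP 5.2: "Twenty imputations will be performed". Protocol 11.4: "One hundred imputations will be performed". SAP section 6 records a different change to this analysis and refers in general terms to clarifications of the sensitivity analyses. It does not list the move from 100 to 20.

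**Tipping point (sensitivity).** SAP 5.2 shifts the as-treated imputed values in the FAB122 arm and says "For each shift the primary analysis method will be repeated on the 20 multiple imputed data sets", although as-treated imputation is set at 100 in the same section. The opening sentence reads "The tipping point is defined as the difference in the change from baseline in ALSFRS-R score at week 48 between FAB122 and placebo"; by this it means the value where significance is gained or lost. The text then describes a search over shifts in steps of 0.2.

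**Not stated.** Neither document gives a seed, a Monte Carlo error tolerance or a reason for 20 in one place and 100 in another.

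**The concern.** A multiply imputed p-value depends partly on random draws. With a finite number of imputations m, a second run on the same locked data with another seed gives a slightly different estimate, standard error and p-value. That is harmless in a descriptive analysis. Here the p-value is compared with a hard 0.05 limit, and the fixed sequence in SAP 4.1 makes the later tests depend on it: if the primary test fails, CAFS at 48 weeks and survival time become exploratory. CAFS also takes missing week-48 scores of survivors from the imputation in SAP 5.6.1.

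With no seed stated, two competent analysts following the SAP could report opposite verdicts on a borderline result, and neither would have departed from the plan. A sponsor could also not show afterwards that the seed had been chosen without sight of the result.

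**Working it through.** **Inputs from the documents.** Difference 3.0, SD 7.5, 200:100, 90% power, tested "at a 5% (2-sided) level of significance" (SAP 2.4); m = 20 for the primary analysis; m = 100 for as-treated imputation.

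**Assumptions.** FMI is not given, so I use 0.05, 0.10, 0.20 and 0.30. Complete-data degrees of freedom are taken as 290.

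**1. The plan's own figure.** Placebo n = (1.960 + 1.282)² × 7.5² × (1 + 1/2) / 3² = 98.5, rounded up to 99, so 297 in total. With 200:100, SE = 7.5 × √(1/200 + 1/100) = 0.919. The expected z is 3.0/0.919 = 3.27 and power is 90.4%. The stated 300 for 90% is reproduced.

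**2. Seed-to-seed SD of z.** With total variance scaled to 1, the pooled estimate varies over seeds with SD √(FMI/m).

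| FMI | m = 20 | m = 100 |
|---|---|---|
| 0.05 | 0.050 | 0.022 |
| 0.10 | 0.071 | 0.032 |
| 0.20 | 0.100 | 0.045 |
| 0.30 | 0.122 | 0.055 |

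The ratio is √5 = 2.24 throughout.

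**3. Chance that one seed gives p ≥ 0.05 when the p-value with unlimited m is 0.04.** Simulated with the pooled estimate ~ N(Q, B/m), the between-imputation variance estimate ~ B × χ²(m−1)/(m−1), total variance W + (1 + 1/m) × that estimate, and Barnard–Rubin degrees of freedom.

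| FMI | m = 20 | 95% range of p, m = 20 | m = 100 |
|---|---|---|---|
| 0.05 | 6% | 0.032–0.053 | 0.02% |
| 0.10 | 16% | 0.029–0.060 | 0.8% |
| 0.20 | 28% | 0.024–0.073 | 6.6% |
| 0.30 | 36% | 0.020–0.086 | 13% |

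Hand check at FMI 0.20, m = 20:
- p = 0.04 is z = 2.054 on the normal scale. Total variance is 0.8 + 1.05 × 0.2 = 1.01, so z becomes 2.054/√1.01 = 2.044.
- Noise from the estimate is 0.100. Noise from the variance is 2.044 × (1.05 × 0.2 × √(2/19)) / (2 × 1.01) = 0.069. Together √(0.100² + 0.069²) = 0.121.
- Rubin df = 19 × (1.01/0.21)² = 439; observed-data df = (291/293) × 290 × (1 − 0.208) = 228; combined 150, critical t 1.976.
- (2.044 − 1.976)/0.121 = 0.56, an upper tail of about 29%, in line with 28%.

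If the reference p of 0.04 is placed on a t scale with (291/293) × 290 × 0.8 = 230 df, z starts at 2.065 and becomes 2.065/√1.01 = 2.055. Then (2.055 − 1.976)/0.122 = 0.65, or about 26%. The convention matters little.

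**4. Away from the limit, m = 20.** With an unlimited-m p of 0.01, crossing 0.05 has a chance below 0.1% for FMI up to 0.30. With p = 0.02 it is 0% at FMI 0.05–0.10, 0.4% at 0.20 and 2.5% at 0.30. With p = 0.10 it is 0%, 0.2% and 1.1% respectively.

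**5. Averaged over trials under the design alternative (expected z = 3.27): chance that two seeds give different verdicts.**

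| FMI | m = 20 | m = 100 |
|---|---|---|
| 0.05 | 1.0% | 0.5% |
| 0.10 | 1.5% | 0.7% |
| 0.20 | 2.5% | 1.0% |
| 0.30 | 3.3% | 1.4% |

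**The case against.** The strongest reply is that nothing here is invalid and that the exposure is rare. Twenty imputations are pre-specified identically in protocol and SAP. Rubin's rules, named in SAP 5.6.1 for the sensitivity analyses, carry a (1 + 1/m) term and a degrees-of-freedom correction for finite m. Step 5 shows two seeds agreeing in about 97% to 99% of trials under the design alternative. FMI may also be low: observed scores are used after treatment discontinuation, ALSFRS-R can be taken by telephone, and protocol 11.4 expects little missing data.

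Most of this stands, and it is why the point is minor. The argument from low FMI stands only in part. Deaths, expected at under 17% by 52 weeks, and true losses to follow-up go through worst-percentile handling combined with multiple imputation. Patients who meet the respiratory-insufficiency criteria leave the study (protocol 6.5 and 8.1.2). FMI is therefore unknown rather than shown to be low, and even at 0.05 the 95% seed range for p = 0.04 reaches 0.053.

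A reader might infer that the contrast between 20 and 100 causes the instability, or that the primary analysis has the fewest imputations. Neither holds. Any finite m leaves some seed dependence: at FMI 0.20 and an unlimited-m p of 0.045, m = 100 still crosses in 27% of seeds and m = 500 in 8%. In the SAP the primary analysis shares its 20 with the hybrid and tipping-point analyses.

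A reader might also take the opening definition of the tipping point as an error, since the between-arm difference at which significance changes is roughly the critical difference (1.96 × 0.919 = 1.80 points under the design assumptions). The same paragraph goes on to identify the shift as the value sought, so this is loose wording in an otherwise clear procedure.

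**Conclusion.** The concern holds as a minor reproducibility gap. It bites only when the result is near 0.05: an unlimited-m p of roughly 0.04–0.06 at FMI 0.05, widening to roughly 0.02–0.09 at FMI 0.30. Inside that band the seed can decide the gatekeeping test; outside it the seed has almost no effect on the verdict.

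The stronger inference, that 20 imputations inflate type I error, is not supported provided the seed is fixed before unblinding. The documents do not show that it will be, and that omission is the real gap.

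Separately, protocol and SAP disagree on the hybrid count (100 against 20), and the tipping-point analysis uses 20 sets of a type of imputation otherwise planned with 100. Both need reconciling.

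The sizes rest on the assumed FMI range, on 290 complete-data degrees of freedom and, for the two-seed figures, on the design effect being true.

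**What to change.** 1. State the random seed for the primary imputation in the SAP, or in a dated programming specification, before unblinding.
2. Raise m for the primary analysis to at least the 100 already planned for as-treated imputation. More costs only computing time: at FMI 0.20, m = 200 brings the seed SD of z to √(0.20/200) = 0.032. No particular number is a threshold.
3. Report the Monte Carlo error of the pooled estimate, √(B/m), beside the primary result.
4. Use the same m for the tipping-point and hybrid analyses, and settle the hybrid count between protocol 11.4 and SAP 5.2.
5. As a clarification, define and report the tipping point as the shift, in ALSFRS-R points, applied to imputed FAB122 values.

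Cost: a few lines in the SAP, either matching protocol wording or an explicit entry in SAP section 6, and some computing time. No patients, visits or design features change. Label: free improvement, severity minor.
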